#### 4.2. Study Overview

**Study population:** The study will be conducted in a diverse population of participants with mild to moderate AD.

**Dose selection**: Qualified participants will be randomly assigned at a 1:1:1:1 ratio to one of the four treatment arms: buntanetap 7.5 mg, buntanetap 15 mg, buntanetap 30mg, and placebo.

**Study Design:** 320 mild to moderate AD participants will be randomized to 7.5 mg, 15 mg, 30mg of buntanetap QD or placebo. If they provide informed consent, they will undergo a Screening Visit, and if they are considered eligible per the inclusion and exclusion criteria, they will proceed to participate in the treatment period. Randomized participants will visit the clinic for the first-time dosing in clinic, followed by an at home dosing period of 12 weeks, with daily administration of 7.5 mg, 15 mg, or 30 mg of buntanetap or placebo. Participants will be required to visit clinics Day 0 (baseline), 6 weeks, and 12 weeks (end-of-trial), where they will

Confidential Page 21 of 57

undergo study procedures that include safety assessments (AE and concomitant medication monitoring, 12-lead ECGs, clinical laboratory testing, vital signs assessments, and physical/neurological examinations) and psychometric tests (ADAS-Cog11, ADCS-CGIC, ADCS-ADL, DSST, MMSE). At the end of blood sampling, the participants will need to stay for a minimum of 1 hour of observation. After all end-of-study procedures are complete, the participant will be discharged to home. A 24-hour follow-up call will occur after all clinical visits to assess the participants current condition and if there are any additional adverse events or questions.

Participants who drop out during the initial 9 weeks at home treatment period will be discontinued and complete an early discontinuation visit as soon as possible following discontinuation. Participants that drop out after the initial 9 weeks will be scheduled for an end of trial visit. If 4 participants are discontinued due to severe adverse events a DSMB safety review will be conducted without interrupting the study.

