# 6.3. Safety and Tolerability Analysis

Safety and tolerability will be assessed with physical examinations, vital signs, clinical laboratory values, 12-lead ECG, use of concomitant medications, and AE reports. The frequencies of adverse events, serious adverse events, and laboratory abnormalities between the participants across the treatment groups will be compared.

Confidential Page 24 of 57

Participants who dropout during the initial 9 weeks at-home treatment period will be discontinued and invited to an Early Discontinuation visit. Participants that drop out after the initial 9 weeks will be scheduled for an end-of-trial visit. If 4 participants are discontinued due to serious adverse events a DSMB safety review will be conducted without interrupting the study.

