#### 9.4.1 End of Trial Visit

This constitutes the participants' last clinical visit during the study. The end of trial visit will consist of the following: admission procedures, blood sampling, all psychometric and safety tests, and discharge procedures. Fasting is required for safety laboratory tests.

Participants should arrive fasted in the morning after an overnight fast. Clinical safety labs will be drawn and sent to the central lab for analysis.

After safety lab, participants will be provided a low-fat light meal before completing functional and cognitive evaluations, a physical and neurological exam, collecting vital signs, ECG, and reviewing and recording adverse events and concurrent medications. Sites should take detailed notes of the contents of all meals provided to the participants.

If no medical or compliance concerns are identified, the participant will move on to the PK sampling phase, which will entail the following procedures:

- 1) Collect initial samples of blood 10ml (hour 0) with venipuncture unless PI deems inappropriate.
- 2) Administer last dose of assigned study drug after the hour 0 sampling.
- 3) Collect blood (10mL) at the 1hr, 2hrs and 4hrs timepoints. Blood should be taken within  $\pm$  10 mins of times.
- 4) Perform the final safety monitoring.

Prior to discharge from the clinic, vital signs should be recorded, and a review of AE(s) and concomitant medications should be conducted. Upon determination by the Investigator (or qualified designee) that the participant is stable, the participant will be discharged. If a participant experiences an unstable AE, please contact the Medical Monitor for guidance on the appropriate course of action to be taken.

Confidential Page 42 of 57

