#### 10 EARLY TREATMENT/STUDY DISCONTINUATION

The investigators at each site will make every reasonable effort to maximize participant retention. However, if an investigator removes a participant from treatment or study, or if a participant declines further treatment or study participation, an early discontinuation visit will be completed as soon as possible following discontinuation.

Ver. 3.1; 09-25-2023

Participants who discontinue from the study prior to completing all protocol procedures may be replaced in consultation with the Sponsor.

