## 10.1 Reasons for Early Discontinuation

Participants or their LARs may withdraw from the study at any time as stated in the informed consent document given to the participant at the time of enrollment. Participants or their LARs should inform sites as soon as such a withdraw decision is made. Participants must also be discontinued from treatment/study for reasons such as the following:

- Adverse experience: The participant has experienced an adverse event that, in the opinion
  of the investigator, requires early discontinuation. This may include abnormal laboratory
  values.
- Death.
- Safety risk: Any participant who becomes a safety risk to themselves during the trial will be withdrawn.
- Protocol violation: The participant fails to meet protocol entry criteria during the study after being randomized or does not adhere to protocol requirements. \*
- Development of suicidal or homicidal ideation requiring hospitalization or confinement.
- Consent is withdrawn. The participants or their LARs wishes to withdraw from the study.
- The study is terminated by the Sponsor/Coordinating Center, alone or at the recommendation of the Data Safety Monitoring Board.
- Lost to follow up. Participant could not be recalled back to conduct follow up visits.
- \* The line item above requires the participant to continue to meet study entry criteria after randomization. This means that assessments conducted at visits post-randomization, such as vital signs, ECG, and laboratory tests, with results that fall outside of the parameters outlined in the Inclusion/Exclusion criteria must be discussed with the Medical Monitor and Study Team.

The investigator and Medical Monitor will review the case to determine whether the participant must be discontinued from the study based on the abnormal value or if it is safe for the participant to continue treatment.

Confidential Page 44 of 57

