# **APPENDIX 1: SCHEDULE OF EVENTS**

Study Period	Screening/Baseline  Day -42 to 0		At-Home Treatment		Unscheduled Visit k	Early Discontinuation Visit
Visit Timing			6 weeks ± 7 days	12 weeks ± 7 days (end-of-trial) b		
Procedure	Screening j (up to 42 days before Day 0)	Baseline (Day 0)	Clinic Visit -	Clinic Visit	Clinic Visit	Clinic Visit
Informed consent	X					
Inclusion and exclusion criteria	X	X				
Demography information	X					
Full physical and neurological examination	X	X	X	X	X	X
Height, Weight, BMI	X					
Medical and psychiatric history (includes substance use)	X					
Urine pregnancy test (WOCBP only)	X	X	X	X	X	X
MMSE 	X	X		X		X
ADCS-CGIC		X d	Xe	Xe		Xe
ADAS-Cog11		X	X	X		X
ADCS-ADL		X	X	X		X
DSST		X	X	X		X
C-SSRS	X	X	X	X	X	X
Safety laboratory tests c	X	X	X	X	X	X
12-lead ECG	X	X	X	X		X
Vital signs a	X	X	X	X	X	X

Confidential Page **56** of **57** 

Protocol ANVS-22002 Ver. 3.1; 09-25-2023

Study Period	Screening/Baseline  Day -42 to 0		At-Home Treatment		Unscheduled Visit k	Early Discontinuation Visit
Visit Timing			6 weeks ± 7 days 12 weeks ± 7 days (end-of-trial) b			
Procedure	Screening j (up to 42 days before Day 0)	Baseline (Day 0)	Clinic Visit	Clinic Visit	Clinic Visit	Clinic Visit
Randomization		X				
Genetic sample (ApoE)		X				
Study intervention		X g	$X^h$	$X^{I}$		
Study intervention compliance review			X	X		
AE/SAE review	X	X	X	X	X	X
Concomitant medication review	X	X	X	X	X	X
PK sampling		X		X		
Sampling for blood biomarkers		X		X		
24-hour phone follow-up		X	X	X	X	X

<sup>a Vital sign will include sitting blood pressure, pulse, temperature, respiration rate.

Confidential Page 57 of 57

<sup>b Participants that drop out before the initial 9 weeks of study treatment will complete the Early Discontinuation visit and participants that drop out after the initial 9 weeks of study treatment will complete the End-of-Trial visit.

<sup>c Safety labs should be taken fasted.

<sup>d ADCS-CGIC evaluation only.

<sup>e ADCS-CGIC evaluation and scoring the scale.

g Participants are given one pill during the visit after taking pre-dose (0h) blood samples and the pills for the remaining 6 weeks at the end of the visit.

<sup>h Participants are given pills for the remaining 6 weeks at the end of the visit.

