8.2.10 Exposure to Treatment

Duration of exposure will be summarized quantitatively using the number of days on study drug for each patient, displayed by treatment group. Duration will be calculated as (last dose date – first dose date + 1).

Compliance with treatment will be assessed as the percentage of tablets taken in relation to number of tablets expected to be taken.

Compliance with study drug (%) =
$$\frac{Total\ number\ of\ tablets\ taken}{Number\ of\ tablets\ expected}$$

Exposure and compliance will be presented using summary statistics by treatment group and the pooled buntanetap-treatment group.

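### After Week 9, the protocol sends a participant who has stopped study drug to a visit with a dose in some sections and to a visit without one in Section 10; a clinic dose would also extend exposure as the SAP counts it

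*Protocol*

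**What the plan says.** **Route to the End-of-Trial visit.** Protocol 6.3: "Participants that drop out after the initial 9 weeks will be scheduled for an end-of-trial visit". Section 4.2 says the same, and Appendix 1 footnote b states that "participants that drop out after the initial 9 weeks of study treatment will complete the End-of-Trial visit". The SAP repeats footnote b in its own Appendix 1.

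**What happens there.** Protocol 9.4.1 lists, as a step of the PK phase, "Administer last dose of assigned study drug after the hour 0 sampling", with blood draws at 1, 2 and 4 hours. Entry to that phase requires that no medical or compliance concern has been identified. The Appendix 1 footnote to the 12-week dosing entry says that one pill is given after the pre-dose sample, and attaches no condition.

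**Route to the Early Discontinuation visit.** Protocol 10 applies "if an investigator removes a participant from treatment or study, or if a participant declines further treatment or study participation, an early discontinuation visit", to be held as soon as possible. It has no Week 9 cut-off. In Appendix 1 the Early Discontinuation column has no mark for study intervention or PK sampling.

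**Mandatory discontinuation.** Protocol 10.1: "Participants must also be discontinued from treatment/study for reasons such as the following". The list includes adverse experience and safety risk.

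**Exposure.** SAP 8.2.10: "Duration will be calculated as (last dose date – first dose date + 1"). SAP Section 7 uses the same formula for the per-protocol set, with a threshold of 67 days. That set supports the primary and secondary analyses.

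**The concern.** Two sites could each follow the protocol and act differently with the same participant, for example one who stops in Week 10. One site would hold an End-of-Trial visit and could give a capsule; the other would hold an Early Discontinuation visit and give none. Whether a person who has come off study drug receives it again should not depend on which section the site reads. It matters most where the stop was mandatory under Section 10.1.

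The second stake is in the data. The exposure formula uses only the first and last dose dates. One capsule in clinic after a gap moves the last dose date, so the off-drug days count as exposure, both in the exposure table and in the test for per-protocol membership.

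**Working it through.** **Step 1: the passages side by side, for a participant who stops after Week 9**

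| Source | Visit | Dose and PK |
|---|---|---|
| Protocol 4.2, 6.3; Appendix 1 footnote b | End-of-Trial | not addressed |
| Protocol 9.4.1 | End-of-Trial | yes, if no medical or compliance concern |
| Appendix 1 dosing footnote, 12 weeks | End-of-Trial | one pill, no condition |
| Protocol 10 with the Appendix 1 column | Early Discontinuation | none |

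Two questions are left open: which visit applies, and whether the dosing and PK steps apply to someone already off drug.

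**Step 2: does the 9.4.1 condition settle it?** The same condition precedes first dosing at Baseline (Protocol 9.2), so it is general wording. It does not define a concern or mention prior discontinuation, and the Appendix 1 footnote omits it.

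**Step 3: exposure.** Inputs: the SAP formula; Day 0 as the day of first dose (protocol numbering); end of Week 9 = Day 63; Week 12 window = Day 84 ± 7, that is Days 77 to 91. The documents do not date a late drop-out's End-of-Trial visit, so the window is an assumption.

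For a last home dose on Day 64, exposure to that dose is 64 − 0 + 1 = 65 days.

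| Clinic dose | Exposure by formula | Excess over 65 | Ratio |
|---|---|---|---|
| Day 77 | 77 − 0 + 1 = 78 | 13 | 78/65 = 1.20 |
| Day 84 | 84 − 0 + 1 = 85 | 20 | 85/65 = 1.31 |
| Day 91 | 91 − 0 + 1 = 92 | 27 | 92/65 = 1.42 |

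**Step 4: the 67-day threshold.** A last home dose on Day 63, 64 or 65 gives 64, 65 or 66 days and falls short. A clinic dose on Day 66 or later gives at least 66 − 0 + 1 = 67 and passes. Crossing the threshold therefore does not need a Week 12 visit, although the size of the overstatement does. A last home dose on Day 66 or later already passes, so only a three-day band of stops can cross.

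**Step 5: how many.** Planned dropout is 0.125 × 320 = 40. Spread evenly over 12 weeks, 40 × 3/12 = 10 fall after Week 9, of whom 10 × 3/4 = 7.5 are on active drug. This takes all 10 as dosed, so it is an upper illustration. On the same basis the three-day band holds about 40 × 3/84 = 1.4 participants.

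**The case against.** **General versus specific.** Section 10 can be read as the general rule and the Week 9 split, stated consistently three times, as the specific one. The words last dose in 9.4.1 also suggest someone still on treatment. That may settle the visit, but not whether a discontinued participant is dosed there. Dropping out is not defined; since Section 10 covers leaving either treatment or study, the overlap remains.

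**The 9.4.1 condition.** Someone who stopped for an adverse event may well raise a medical concern. On compliance, the Day 64 example has 65 of 92 daily doses (71%) by Day 91 and 65 of 85 (76%) by Day 84, both under the encouraged 80% in Protocol 7.6; by Day 77 it is 65 of 78 (83%). Some participants would therefore be held back, and this part of the objection stands. But 80% is an encouragement, and no text makes a shortfall a bar to dosing. Participants may also refuse the capsule.

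**Stronger readings that a reader might infer.**
- *That the protocol requires re-dosing of people withdrawn for adverse events.* It does not: 9.4.1 leaves room to withhold.
- *That a clinic dose restarts the adverse-event window of last dose plus 30 days in Protocol 6.12.* The SAP definition (8.2.2, 8.3.1) has no such window, and SAP Section 3 makes the SAP the ruling document. Collection also ends at the 24-hour call (Protocol 14.1), at about Day 92 for a Day 91 visit, before 64 + 30 = Day 94. No collected event changes class.
- *That Week 12 PK is seriously distorted.* With the longest plasma half-life in Protocol 3.2, 5.23 hours, and assuming first-order elimination, once-daily accumulation is 1/(1 − 2^(−24/5.23)) ≈ 1.04. Half-life at low doses could not be calculated accurately, so this is an extrapolation, but the effect is probably small. The parameter analysis is in a separate PK SAP, so pooling of such profiles cannot be confirmed.
- *That exposure is generally overstated by about 40%.* That is the Day 91 extreme; a prompt visit leaves a gap of days.

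**Conclusion.** The contradiction is real. After Week 9 the protocol gives two answers on the visit and, through it, on dosing and PK sampling; the condition in 9.4.1 narrows the conflict without resolving it. This rests on the text alone.

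The consequence for the analysis is definite in kind and limited in size. In the Day 64 example one clinic dose adds 13 to 27 days if the visit is in the Week 12 window, and fewer if it is earlier. It can move a participant across the 67-day threshold, but only for stops in a three-day band, and membership also depends on protocol deviations. The count of about 10 rests on even dropout and on all being dosed.

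The primary ITT analysis does not use exposure, and 9.4.1 places the cognitive and functional assessments before the dose, so the documents do not support reading this as a threat to the primary result. The reason to correct it is that sites need one instruction on whether a discontinued participant receives study drug.

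**What to change.** **Protocol.** Reconcile 4.2, 6.3, 9.4.1, Section 10 and Appendix 1 (footnote b and the 12-week dosing footnote; likewise the SAP's copy of the schedule) so that they give one answer to each question: which visit applies after Week 9, and whether the dosing and PK steps apply to someone who has already stopped study drug. State whether the 9.4.1 condition covers prior discontinuation, and make the dosing footnote agree with it. The clinical team decides the rule.

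**SAP.** In 8.2.10 and in the 67-day rule of Section 7, end exposure at the last dose before discontinuation, so that a single clinic dose after a gap does not count off-drug time.

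**PK SAP (minor).** Flag Week 12 profiles taken after a dosing gap.

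**Cost.** A protocol clarification, two SAP sentences and one data flag. No extra visits or participants.

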# 6.4. PK Analysis

Plasma concentration-time data will be analyzed by non-compartmental methods using SAS version 9.4 or greater. Calculations will be based on the actual sampling times recorded during the study. Since the study is blinded, all participants' plasma will be included in the PK analysis. From the plasma concentration-time data, the following PK parameters will minimally be determined, as data permit: Area under the curve (AUC), Cmax, Tmax, t½, and CL. Dose-proportionality may be calculated on Cmax and AUC as appropriate.

Plasma concentration-time data for buntanetap will be listed and summarized descriptively (number of participants (N), mean, median, standard deviation (SD), minimum (min), and maximum (max)) and graphically presented. PK parameters will be listed and summarized descriptively (N, mean, median, SD, min, max, and 95% CI) by each dose regimen. In addition, geometric means, and between-participant coefficients of variation (CV) will be calculated.

#### 6.5. Criteria for Termination of the Trial

The trial may be terminated by the Sponsor based on issues of safety, and Data Safety Monitoring Board (DSMB) recommendations.

An independent Data Monitoring Board (DSMB or IDMB) will be formed to safeguard the participants' wellbeing. The responsibilities of IDMB will be established in the IDMB Charter. The study will have a safety analysis when 90 randomized participants (about 30% of the targeted sample size) have been treated for 6 weeks.

# 6.6. Statistical Analysis

Continuous variables will be summarized using the following descriptive statistics: number of subjects, mean, median, standard deviation (SD), standard error (SE), minimum, and maximum. Unless otherwise specified, means, medians and confidence intervals (CIs) will be presented to one more decimal place than the raw data, and the SD and SE will be presented to two more decimals than the raw data. In general, the maximum number of decimal places is 4. Wherever possible, data will be decimally aligned.

Categorical variables will be summarized by the number of subjects and the percentage of subjects in each category. Categories with zero counts will not have zero percentages displayed. For demographic summaries, percentages will be calculated by using the total number of subjects in the given treatment group as the denominator. Percentages will be presented with one decimal place.

Confidential Page 25 of 57

Ver. 3.1; 09-25-2023

Unless otherwise specified, all statistical tests will be 2-sided at the significance level of 5% and all the Cis will be 2-sided 95%. P-values will generally be presented to 4 decimal places; values less than 0.0001 will be presented as <0.0001.

Confidential Page 26 of 57

Ver. 3.1; 09-25-2023

# 6.7. Study Participants and Demographics

# 6.7.1 Population Analysis Set

Enrolled Analysis Set: The enrolled population will include all participants who signed Informed Consent and meet all inclusion and exclusion criteria.

Randomized Analysis Set: The Randomized Analysis Set (RAS) consists of all participants who were randomized. Subjects will be classified according to the randomized treatment assignments.

Safety Analysis Set: The Safety Analysis Set (SAS) consists of all randomized participants who received at least one dose of study drug. Subjects will be analyzed according to the actual treatment.

Full Analysis Set: The Full Analysis Set (FAS) consists of all participants who were randomized, received at least one dose of study drug, and have both a baseline and at least one post-baseline value for the ADAS-Cog11 or ADCS-CGIC score after taking study drug. Subjects will be analyzed according to the treatment they were randomized.

Per Protocol Analysis Set: The Per-protocol Analysis Set consists of all participants in the FAS who do not have major protocol deviation. The membership of this analysis set will be determined prior to database lock.

# 6.7.2 Disposition and Withdrawals

The numbers of participants screened, randomized, completing, discontinuing treatment, and withdrawing, along with reasons for discontinuation or withdrawal, will be tabulated overall and by treatment group. The number of participants in each analysis population will be reported.

#### 6.7.3 Protocol Deviations

Major protocol deviations will be classified and documented before database lock and will be discussed in the CSR. All protocol deviations, both minors and majors, will be presented in a data listing.

#### 6.7.4 Demographics and Other Baseline Characteristics

Demographic and baseline characteristics (including age, sex, race/ethnicity, weight, and height) will be summarized for each treatment group and for the overall population by descriptive statistics.

#### 6.7.5 Medical History and Concomitant Medications

Medical history will be listed. Prior and concomitant medications will be summarized by treatment group, by the number and percentage of participants taking each medication, classified using World Health Organization (WHO) Drug Dictionary Anatomical Therapeutic Chemical (ATC) classes and preferred terms.

Confidential Page 27 of 57

# 6.8 Analysis of Primary Endpoints

The co-primary endpoints are the change from baseline to 12 weeks in ADAS-Cog11 scores and the ADCS-CGIC scores at 12 weeks. The ADAS-Cog11 will be analyzed via mixed models for repeated measures (MMRM). The model for ADAS-Cog11 will include treatment, timepoint, treatment-by-timepoint interaction as the fixed effects, baseline ADAS-Cog11as the covariate, and subjects as random effect. The Model for ADCS-CGIC will include treatment, timepoint, treatment-by-timepoint interaction as the fixed effects, and subjects as random effect. An unstructured covariance matrix will be used and the Kenward-Roger approximation will be used to adjust the denominator degrees of freedom. The change from baseline and the differences in the change from baseline between treatments will be based on the Least Square Means from this model. The two-sided 95% confidence intervals of the treatment differences will be presented.

Ver. 3.1; 09-25-2023

